⁴Estradiol vaginal tablet (Vagifem[®]): one tablet (10 microgram) inserted daily into the vagina for two weeks (fourteen days) then 1 tablet inserted intravaginally twice weekly for 24 + 2 additional weeks.

Data Collection & Management:

Baseline data will include the following:

- Patient age, race, vaginal parity, menopausal state, BMI, history of previous use of vaginal estrogen
- FSFI, DIVA, and UDI-6 questionnaires
- VAS for GSM symptoms and VHI for objective GSM findings

Data points recorded during the procedure will include:

- Likert Scales for physician assessment of patient comfort during the procedure.
- Adverse events including inability to complete the procedure due to discomfort or constricted vagina

Post-procedure data will include the following:

- The rate of satisfaction of patients with treatment by mean of the Patient Global Impression of Improvement (PGI), using a 5-point Likert scale.
- The degree of difficulty encountered by the physician in performing the treatment, by mean of a 5-point Likert scale.
- Additionally, untoward side effects of treatment such as new bothersome vaginal irritation and significant vaginal bleeding will be recorded.

Protection of each subject's personal health information will be a priority in this study. One master Excel file containing subject personal information including name and medical record number will be kept in a password-protected file, on a designated protected research drive on a password-protected computer in a locked office at each respective institution. In that file, each subject will be assigned a subject identification number that will be used for the purposes of data collection in order to de-identify subjects.

All paper forms used for data collection will be kept in a research cabinet dedicated to this project, which will be locked at all times, in a locked office at the Cleveland Clinic (or other institution). All forms will contain de-identified information. Identification numbers will correspond to the subjects listed in the master excel file.

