All study data will be transferred and managed electronically using REDCap (Research Electronic Data Capture). Each subject will be entered into REDCap using the assigned identification number from the master excel file. REDCap is a secure, web-based application designed to support data capture for research studies, providing user-friendly web-based case report forms, real-time data entry validation, audit trails, and a de-identified data export mechanism to common statistical packages. The system was developed by a multi-institutional consortium which was initiated at Vanderbilt University and includes the Cleveland Clinic. The

database is hosted at the Cleveland Clinic Research Datacenter in the JJN basement and is managed by the Quantitative Health Sciences Department. The system is protected by a login and Secure Sockets Layers (SSL) encryption. Data collection is customized for each study as based on a study-specific data dictionary defined by the research team with guidance from the REDCap administrator in Quantitative Health Sciences at the Cleveland Clinic.

Statistical Analysis Plan

Sample Size Rationale

We plan to enroll and randomize 196 patients in this non-inferiority trial comparing vaginal estrogen therapy to laser treatment of vaginal atrophy. The primary outcome will be subjective assessment of vaginal dryness as assessed by 10 cm visual analog scale at 6 months after initiating treatment. Assuming an alpha of 0.025 and a standard deviation of 2.0 [24], 85 subjects in each group will provide a 90% power to reject the null hypothesis (H0) that the true difference in vaginal dryness VAS score (Vaginal Estrogen – Vaginal Laser) is less than or equal to 1.0 cm on the VAS (effect size 0.5) in favor of the alternative hypothesis (H1): the true difference is greater than 1.0 cm using a one sided two sample t-test. Anticipating a 15% loss to follow-up and/or drop-rate over the period of the study, the total enrollment goal is 196 participants.

Analysis Plan

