This study is a non-inferiority study design. The predefined non-inferiority margin is a difference of 1.0cm on a 10cm VAS. To minimize bias towards a finding of non-inferiority, data from women who were eligible and received the assigned treatment (per protocol) will be used for the analysis of the primary outcome. The primary outcome will be presented as the difference in VAS scores between treatments (Vaginal Estrogen – Vaginal Laser). The hypothesis of non-inferiority of the two treatment groups will be tested by comparing the lower limit of the two-sided 95% confidence interval (equivalent of a one-sided significance level of 0.025%) of the absolute difference with the margin set at -1.0cm. A secondary analysis of the primary outcome according to original treatment assignment (intent to treat) will also be performed as well as standard superiority testing using Student's t-test. If differences in baseline patient characteristics are noted, linear regression analysis adjusting for these differences will also be performed. Secondary outcomes will be analyzed using the intent to treat population using Pearson's Chi-square test for categorical data, Student's t-test for parametric continuous data, or Wilcoxon rank sum test for ordinal or nonparametric continuous data. Changes in patient reported outcome questionnaires (FSFI, DIVA, UDI-6, etc.) will be compared between treatments using repeated measures ANCOVA.

SAFETY AND ADVERSE EVENTS

Definitions

Adverse events include prolonged vaginal bleeding beyond 48 hours, heavy vaginal bleeding, bothersome vaginal irritation, bacterial vaginosis, vaginal yeast infection, post-procedural fever, and skin burn.

Recording of Adverse Events

At each contact with the subject, the investigator will seek information on adverse events by specific questioning and, as appropriate, by examination. Information on all adverse events will be recorded immediately in the source document, and also in the appropriate adverse event section of the case report form (CRF). All clearly related signs, symptoms, and abnormal diagnostic procedures results will also be recorded in the source document.

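### The enrolment goal of 196 does not keep 85 women per arm after the plan's own 15% loss: about 83 per arm remain, with about 89.3% power instead of 90%

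*Combined protocol and SAP*

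**What the plan says.** All the linked figures are in one paragraph, the Sample Size Rationale of the Statistical Analysis Plan (combined protocol and SAP).

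- Number randomised: "We plan to enroll and randomize 196 patients in this non-inferiority trial".
- Size and power: "85 subjects in each group will provide a 90% power to reject the null hypothesis". The paragraph gives a one-sided alpha of 0.025, a standard deviation of 2.0 cm and a distance of 1.0 cm (effect size 0.5), with the test described as "using a one sided two sample t-test".
- Allowance for loss: "Anticipating a 15% loss to follow-up and/or drop-rate over the period of the study, the total enrollment goal is 196 participants".

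The Analysis Plan that follows adds two relevant points. On the margin: "The predefined non-inferiority margin is a difference of 1.0cm on a 10cm VAS", applied as −1.0 cm to estrogen minus laser. On the analysis set: "data from women who were eligible and received the assigned treatment (per protocol) will be used for the analysis of the primary outcome".

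The plan does not show how 196 was obtained and does not state the true difference assumed for the power calculation.

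**The concern.** A loss allowance exists so that the number needed for the stated power is still there at the end. Here 85 per group is needed, a 15% loss is expected and 196 women are randomised. Applied to those randomised, the loss leaves fewer than 85 per group, so the plan does not deliver its stated power at its own stated loss rate.

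The 85 has no spare margin: by the exact t calculation it gives 89.99% power, so any shortfall takes power below 90%. The paragraph also does not say whether its 15% covers women dropped from the per-protocol primary analysis because they were ineligible or did not receive the assigned treatment. What is at stake is an evaluable number and a power figure that are slightly too favourable. The validity of the test is not affected.

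**Working it through.** **Inputs.** From the Sample Size Rationale: one-sided alpha 0.025, SD 2.0 cm, distance 1.0 cm, 85 per group, 90% power, 15% loss, 196 randomised. From the Analysis Plan: margin −1.0 cm. Two assumptions are added: a true difference of zero (not stated, but the value at which 85 per arm gives 90%) and 1:1 allocation (implied by the equal group sizes), so 98 women are randomised per arm.

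**1. Reproduce the plan's 85 and 90%.**

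Normal approximation: n per arm = 2 × (1.960 + 1.282)² × 2.0² / 1.0² ≈ 84.1, rounded up to 85. This agrees with the plan.

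Exact power of the two-sample t-test: with df = n₁ + n₂ − 2 and noncentrality λ = 1.0 / (2.0 × √(1/n₁ + 1/n₂)), power is the probability that a noncentral t variable with parameters (df, λ) exceeds the 97.5th percentile of the central t distribution. At 85 + 85, λ = 1.0 / (2.0 × √(2/85)) = 3.26 and power is 0.8999. The plan's 90% is confirmed.

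**2. Apply the plan's loss rate to its enrolment goal.**

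- Women remaining: 196 × 0.85 = 166.6, or 98 × 0.85 = 83.3 per arm.
- Enrolment needed to keep 170: 170 / (1 − 0.15) = 200.
- Largest loss at which 196 keeps 170: 1 − 170/196 = 13.3%.
- A route that gives 196: 170 × 1.15 = 195.5, rounded up. This adds 15% to the required number instead of dividing by 0.85. It is the likely origin, but the plan does not say so.

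**3. Power at the number that remains (true difference zero).**

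| Evaluable women | Exact t | Normal approximation |
|---|---|---|
| 85 + 85 | 90.0% | 90.3% |
| 83 + 84 | 89.5% | 89.8% |
| 83 + 83 | 89.3% | 89.6% |

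The cost is 0.5 to 0.7 points, depending on how 166.6 is rounded.

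**4. Does the gap depend on assuming zero difference?** If laser is truly worse by the amounts below (assumed values), the exact t power is:

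| True difference against laser | 85 per arm | 83 per arm | Gap |
|---|---|---|---|
| 0 | 90.0% | 89.3% | 0.7 points |
| 0.1 cm | 83.1% | 82.2% | 0.9 points |
| 0.2 cm | 73.7% | 72.6% | 1.0 points |

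The level of power moves a good deal, but the cost of the mismatch stays between 0.7 and 1.0 points.

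**5. If per-protocol exclusions come on top of the 15%.** The documents give no rate, so 5% and 10% in both arms are assumed for illustration.

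- 98 × 0.85 × 0.95 = 79.1, about 79 per arm: 87.8% power.
- 98 × 0.85 × 0.90 = 74.97, about 75 per arm: 86.0% power.

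**The case against.** The strongest reply is that nothing is really wrong. The plan never says in so many words that 85 per arm will remain after loss. It says that 85 per arm gives 90% power, which is right, and then separately sets a goal of 196. If the 15% is read as an addition to the required 170, every figure reconciles. The gap is 4 in 200, the loss rate is itself only a forecast, and 83 + 83 is the less favourable rounding, since 167 women (83 + 84) would give 89.5%.

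The point about size stands: this is a small correction, not an underpowered trial. The add-on reading does not rescue the text. The 15% is described as a loss over the course of the study, and 196 is the number randomised, so the natural base is the women randomised. On the add-on reading the loss rate would be 13.3%, which the plan does not say.

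A second reply is that the power figures rest on a reading of the hypothesis. The Sample Size Rationale prints the null as a difference of at most 1.0 cm, whereas the Analysis Plan puts the margin at −1.0 cm. Taken literally with a true difference of zero, the printed null gives almost no power. That is fair and needs saying. The −1.0 cm margin is used here because, at a true difference of zero, it is the reading that reproduces the plan's own 90% at 85 per arm. The mismatch among 196, 15% and 85 does not depend on the margin.

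It is also fair that the 5% and 10% exclusion rates have no basis in the documents, and that the 15% may already include such exclusions. They support a request for clarification and no more.

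**Conclusion.** The concern holds and is minor. A 15% loss from 196 leaves about 167 women, about 83 per arm, not 170. Confidence is high for that mismatch, which is plain arithmetic on figures in one paragraph. Nothing else in the documents reconciles them.

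The consequence is about 0.7 power points (89.3% against 90.0%) if the true difference is zero, and up to 1.0 point if laser is truly worse by up to 0.2 cm. These power figures assume 1:1 allocation, SD 2.0 cm, one-sided alpha 0.025 and the −1.0 cm margin. The required 85 per arm is correct; the error lies in the step from 170 to 196. No analysis or decision rule is affected.

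**What to change.** Restate the sentence in the Sample Size Rationale along these lines: 196 women randomised; after a 15% loss about 83 per arm are expected, giving about 89% power if there is no true difference between treatments. Two other statements would also be consistent: keep 196 and 85 per arm but give the allowance as 13.3%, or keep 15% and set the goal at 200. The restatement is enough and needs no extra patients.

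Add one sentence saying whether the 15% includes women left out of the per-protocol primary analysis.

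The cost is one restated sentence and one clarifying sentence, with no extra visits or data.

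Optional, and not part of this correction: prespecify adjustment of the primary comparison for baseline dryness VAS. Data Collection & Management already lists it among the baseline data: "VAS for GSM symptoms and VHI for objective GSM findings". The Analysis Plan currently offers regression adjustment only if baseline differences are noted. No power gain is claimed, because the documents give neither the correlation between baseline and 6 months nor whether 2.0 is the SD of the 6-month score or of the change. This would alter the primary model, so it would have to be fixed in the SAP before outcome data are seen.

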Choice of therapy for GSM depends on symptom severity and treatment efficacy and safety. First-line treatment for symptomatic women with GSM, recommended by the North American Menopause Society, includes vaginal moisturizers, vaginal lubricants, and continued sexual activity. If these therapies fail, estrogen treatment should be considered in patients without contraindications. Topical estrogen therapy is designed to temporarily alleviate symptoms and reverse atrophic anatomical changes [14]. Despite proven effectiveness with symptom relief [14, 15], compliance rates for estrogen are variable, ranging between 52-74% [16]. Furthermore, long-term data (> 1 year) of these topical estrogen therapies are lacking. [15]. Additionally, no information is available in high-risk patients [14], e.g. those with known breast or uterine cancer in whom estrogen therapy is relatively contraindicated and where the management depends on a woman's preference, potential benefits, understanding of potential risks, and recommendations from oncology specialists [14].

Fractional CO₂ lasers have demonstrated safety and remodeling tissue properties in many body regions, such as the skin of the face, neck and chest, with the effect of producing new collagen and elastic fibers [17-20]. Moreover reports on the use of Er:YAG laser, similar to a CO₂ laser for its superficial effect, showed improvement in two aspects of pelvic floor dysfunction (urinary incontinence and vaginal laxity) [21,22]. Recently, the regenerative effects of intravaginal fractional CO₂ laser on the vaginal epithelium and lamina propria in postmenopausal women with GSM has been reported by Salvatore *et al* [23]. The same investigators found that microablative fractional CO₂ laser was feasible, efficacious, and safe in improving GSM symptoms in postmenopausal women at 12-week follow-up [24]. Additionally, intravaginal fractional CO₂ laser therapy caused a significant decrease in the severity of dyspareunia related to vaginal dryness in these patients, and was subsequently associated with a consistent improvement in sexual function and sexual satisfaction of menopausal women with GSM [25, 26].

Hypothesis: The CO₂ fractional vaginal laser therapy is non-inferior to vaginal estrogen therapy in the treatment of GSM.

Study Design and Aim:

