In addition to a standardized evaluation including the history and physical examination, patients will be asked to complete the Female Sexual Function Inventory (FSFI) questionnaire, the Day-to-day Impact of Vaginal Aging (DIVA) questionnaire, and the Urogenital Distress Inventory (UDI-6), at baseline, 3 months, and 6 months after baseline and visual analog scales (VAS) for GSM symptoms. The Patient Global Index (PGI) will also be administered at 6 months. Completion of these questionnaires should take no more than 15-20 minutes. A vaginal maturation index will be obtained at the baseline visit on a regular Pap Smear slide and fixed with cytofixative and air dried. This will be repeated during the last follow up visit at 6 months.

Vaginal Laser Protocol

Postmenopausal women will undergo treatment intravaginally with the fractional microablative CO₂ laser system (SmartXide 2 V 2 LR, MonaLisa Touch, DEKA, Florence, Italy), using the following setting: dot power 30 watt, dwell time 1000 μ s, dot spacing 1000 μ m and the smart stack parameter from 1 to 3. Stack 1 is used at baseline and stack 3 at 6 weeks and 3 months. The laser beam will be applied using a 90° vaginal probe gently inserted up to the top of the vaginal canal and subsequently withdrawn at centimeter intervals and rotated to 6 positions in an alternating clockwise and counterclockwise pattern in order to provide a complete treatment of the vaginal wall. At the investigators discretion a flat probe (vulvar probe) may be utilized to more efficiently treat the introital area and vestibule. At the level of the vaginal introitus, the dot power will be decreased to 26 watts. A treatment cycle includes three laser applications (every 40-50 days, approximately 6 weeks). The procedure will be performed in the outpatient clinic and does not require any specific preparation (e.g. analgesia/anesthesia). At the clinician's discretion, EMLA cream may be applied to introitus for thirty minutes and wiped clean and dried prior to vulvar laser therapy. Patients will be recommended to avoid coital sexual activity for at least 3 days after each laser application because a mild inflammatory reaction may last up to 48 hours after laser therapy. Topical lidocaine 5% ointment may be used for any vulvar pain post-procedure.

Post Treatment Instructions

- Each subject shall be evaluated immediately post-treatment for complications and side effects, excessive bleeding, symptomatic vaginal discharge, pain, etc.

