- Patient evaluation of the overall treatment (PGI) using a 5-point Likert scale will be conducted at 6 week, 3 month and 6 month follow-up visits.
- After each treatment, the PI or co-investigator will be asked to evaluate the ease of treatment using a 5-point Likert scale.
- After each treatment, the subject will be asked the degree of discomfort experienced as a result of treatment using a 5-point Likert scale.
- Events will be evaluated and recorded.

Questionnaires and evaluations

Questionnaires will be administered by a **research nurse coordinator who is blinded to the patient's therapy**. Sexual function, GSM, and urinary function will be evaluated with the 10-cm VAS, Female Sexual Function Index (FSFI), Day-to-day Impact of Vaginal Aging (DIVA), and Urogenital Distress Inventory (UDI-6), both at baseline prior to 1st laser treatment or commencing with vaginal estrogen (depending on treatment group), and at 12 weeks from

baseline (+/- 1 week) but prior to 3rd laser treatment (if applicable), and at 3 months follow-up after 3rd laser treatment (if applicable). Note that all patients will follow up 6 months from baseline visit for final assessment

The DIVA questionnaire will be administered at baseline, 3 month, and 6 month follow-up visit period, in addition to the FSFI, UDI-6, VHI, and PGI during final assessment. All questionnaires are supplied in the appendix.

Calendar of Study Procedures

	Baseline	6 weeks	3 months	6 months
Informed Consent	X			
H & P	X			
MonaLisa Touch vaginal laser ¹	X	X	X	
Vaginal estrogen therapy ^{2, 3, 4}	X	X	X	
Vaginal symptom VAS	X	X	X	X
Vaginal health index VHI	X	X	X	X
Vaginal maturation index	X			X
DIVA questionnaire	X		X	X
Vagina dilator calibration	X	X	X	X
FSFI	X		X	X
UDI-6	X		X	X
Likert scale (laser patient)	X	X	X	
PGI		X	X	X
Likert scale (laser provider ease)	X	X	X	
Adverse events	X	X	X	X
Sexual activity	X	X	X	X

¹A treatment cycle includes three laser applications (every 5-7 weeks).

²Conjugated estrogen cream (Premarin[®]): 0.5g of cream intravaginally daily (using applicator or fingertip) for two weeks (fourteen days) then 0.5 g twice weekly for 24 ± 2 additional weeks, **or**

³Estradiol cream (ESTRACE[®]): 1.0 g of cream intravaginally daily (using applicator or fingertip) for two weeks (fourteen days) then 1.0 g twice weekly for 24 + 2 additional weeks, **or**

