Appendix

Baseline Examination Data

Pt. ID # _____

Treatment Group

Vaginal Laser Vaginal Estrogen

Age _____ BMI _____

Race

Caucasian African-American Hispanic Asian

Other, specify _____

Marital status

Single Married Divorced Widowed

Menopausal Status

Premenopausal Perimenopausal Postmenopausal (no menses for 6 months)

Current use of oral or transdermal hormonal therapy

Yes No

History of vaginal estrogen use

Yes No

Sexually active

Yes No

Exam:

Vaginal pH _____

Vaginal caliber XS S M L XL

Maturation Index Results:

_____ Data prior to and after Vaginal Laser or Vaginal Estrogen therapy (6 wk, 3 mos, 6 mos):

Exam

Vaginal pH _____

Vaginal caliber XS S M L XL

Local anesthetic used? Yes No N/A (Estrogen arm)

Vulvovestibular laser therapy? Yes No N/A (Estrogen arm)

Adverse event laser arm:

Inability to complete the procedure due to discomfort or constricted vagina

Yes No

Other: Specify _____

PATIENT ID: _____

PATIENT GLOBAL IMPRESSION OF IMPROVEMENT

Patient Global Impression of Improvement

Circle how you feel your symptoms are after treatment:

Much Worse	Worse	Same	Better	Much Better
1	2	3	4	5

Level of satisfaction after treatment

How would you define the level of satisfaction with the treatment?

Very Dissatisfied	Dissatisfied	Same	Satisfied	Very Satisfied
1	2	3	4	5

10 cm VISUAL ANALOG SCALE (VAS)

0 indicating absent symptoms (no bother) and 10 indicating the worst the symptoms could be (bothers as much as you can imagine). Please indicate your degree of bother with an X marked on the 10 cm line below next to each symptom.

	No Bother	Mild Bother	Moderate Bother	Most Bother
Vaginal dryness	0			10
Vaginal itching	0			10
Vaginal irritation	0			10
Painful urination	0			10

Additional question regarding sexual function not included in the FSFI.
This question will be asked at baseline, 6 weeks, 3 months, and 6 months.

Over the past 4 weeks have you been sexually active? (yes/no)

The reason if your answer no

- no partner
- no interest
- due to pain
- due to other reason, please specify_____

VAGINAL HEALTH INDEX SCALE

	Overall elasticity*	Fluid secretion type & consistency	pH	Epithelial mucosa	Moisture
1	None	None	6.1	Petechiae noted before contact	None, mucosa inflamed
2	Poor	Scant, thin yellow	5.6 – 6.0	Bleeds with light contact	None, mucosa not inflamed
3	Fair	Superficial, thin white	5.1 – 5.5	Bleeds with scraping	Minimal
4	Good	Moderate, thin white	4.7 – 5.0	Not friable, thin mucosa	Moderate

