- Moderately satisfied
- About equally satisfied and dissatisfied
- Moderately dissatisfied
- Very dissatisfied

15. Over the past 4 weeks, how **satisfied** have you been with your sexual relationship with your partner?

- Very satisfied
- Moderately satisfied
- About equally satisfied and dissatisfied
- Moderately dissatisfied
- Very dissatisfied

16. Over the past 4 weeks, how **satisfied** have you been with your overall sexual life?

- Very satisfied
- Moderately satisfied
- About equally satisfied and dissatisfied
- Moderately dissatisfied
- Very dissatisfied

17. Over the past 4 weeks, how **often** did you experience discomfort or pain during vaginal penetration?

- Did not attempt intercourse
- Almost always or always
- Most times (more than half the time)
- Sometimes (about half the time)
- A few times (less than half the time)
- Almost never or never

18. Over the past 4 weeks, how **often** did you experience discomfort or pain following vaginal penetration?

- Did not attempt intercourse
- Almost always or always
- Most times (more than half the time)
- Sometimes (about half the time)
- A few times (less than half the time)
- Almost never or never

19. Over the past 4 weeks, how would you rate your **level** (degree) of discomfort or pain during or following vaginal penetration?

- Did not attempt intercourse
- Very high
- High
- Moderate
- Low
- Very low or none at all

Thank you for completing this questionnaire

Medicine Compliance Log:

Weeks 1 and 2, please place an X in the box for each day you inserted vaginal cream or tablet

Weeks 3-6

Weeks 7-12

Weeks 13-18

Weeks 19-24

Urogenital Distress Inventory (UDI-6 Short Form): UDI-6

- 1) Do you usually experience frequent urination? Yes No
If yes, how much does this bother you? Not at all Somewhat
Moderately Quite a bit
- 2) Do you usually experience urine leakage associated with a feeling of urgency; that is, a strong sensation of needing to go to the bathroom? Yes No
If yes, how much does this bother you? Not at all Somewhat
Moderately Quite a bit
- 3) Do you usually experience urine leakage related to coughing, sneezing, or laughing?
Yes No
If yes, how much does this bother you? Not at all Somewhat
Moderately Quite a bit
- 4) Do you experience small amounts of urine leakage (that is, drops)? Yes No
If yes, how much does this bother you? Not at all Somewhat
Moderately Quite a bit
- 5) Do you experience difficulty emptying your bladder? Yes No

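### Non-inferiority is concluded from the per-protocol set alone; the planned intention-to-treat analysis has no say in the decision

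*Combined protocol and SAP*

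**What the plan says.** The Analysis Plan sets a margin of 1.0 cm on the 10 cm dryness scale. It compares the lower limit of the two-sided 95% confidence interval for Estrogen minus Laser with -1.0 cm. The analysis set is per protocol: "data from women who were eligible and received the assigned treatment (per protocol) will be used for the analysis of the primary outcome". The stated reason is to limit bias in favour of non-inferiority.

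ITT appears in one sentence: "A secondary analysis of the primary outcome according to original treatment assignment (intent to treat) will also be performed". No section says that ITT must also clear -1.0 cm, or what is concluded if the two sets differ.

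Membership is described only by eligibility and receipt of treatment, with no minimum exposure in either arm. The Vaginal Laser Protocol describes a course of several sessions: "A treatment cycle includes three laser applications (every 40-50 days, approximately 6 weeks"). The Vaginal Estrogen Protocol runs for two weeks of daily dosing plus about 24 weeks of twice-weekly dosing. The data that could define membership are collected. Data Collection & Management records "Adverse events including inability to complete the procedure due to discomfort or constricted vagina", the Appendix has a matching tick box, and the Medicine Compliance Log asks women to "please place an X in the box for each day you inserted vaginal cream or tablet". None of these is tied to the per-protocol set.

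**The concern.** A per-protocol comparison is no longer a comparison of the randomised groups, and here the two arms can lose women by different routes. A woman may leave the laser group because the procedure could not be completed. A woman may leave the estrogen group because she stopped using the cream or tablet.

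Lower scores are better and the contrast is Estrogen minus Laser. Dropping laser women who did badly lowers the laser mean, raises the difference and moves the result towards non-inferiority. Dropping estrogen women who did badly moves it the other way. The net direction depends on a membership rule that the plan does not state, so the choice of set cannot by itself deliver the protection the plan wants from it.

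Women know their arm and rate their own dryness, so both staying on treatment and the score may be related to assignment. If the two analyses disagree, the plan as written still supports a claim of non-inferiority from per protocol, and the weight given to ITT would be settled after the results are known.

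**Working it through.** **Inputs.** From the Sample Size Rationale: one-sided alpha 0.025, SD 2.0 cm, 85 per group, 90% power, 15% loss, 196 randomised. From the Analysis Plan: limit -1.0 cm for Estrogen minus Laser. Assumed, because the documents give no figures: the share excluded from per protocol in each arm, and how much worse excluded women score than those retained (1 or 2 cm).

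**The plan's own figure.** With a true difference of 0:

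n per arm = 2 × SD² × (z0.975 + z0.90)² / margin² = 2 × 4 × (1.960 + 1.282)² / 1² = 84.06, rounded up to 85.

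Power at 85 per arm is 90.0% (noncentral t). Enrolment: 170 × 1.15 = 195.5, so 196, or 98 per arm. After 15% loss, 98 × 0.85 = 83 per arm, where power is 89.3%. The plan reproduces. It makes no separate allowance for per-protocol exclusions.

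**How exclusions shift the result.** Let fL and fE be the shares excluded from the laser and estrogen arms, and g the gap in cm.

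Per-protocol difference minus ITT difference = g × (fL − fE).

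With 8 of 83 laser women excluded and no estrogen women, the shift is 8/83 × 1 = +0.096 cm, or 8/83 × 2 = +0.193 cm. The standard error with 75 and 83 women is 2.0 × √(1/75 + 1/83) = 0.319 cm.

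**Chance that per protocol shows non-inferiority when the true ITT difference is -1.0 cm** (noncentral t, nominal 2.5%):

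| Excluded, laser / estrogen | Shift, 1 / 2 cm gap | Chance, 1 / 2 cm gap |
|---|---|---|
| 10% / 0% | +0.096 / +0.193 | 4.8% / 8.7% |
| 10% / 10% | 0 / 0 | 2.5% / 2.5% |
| 10% / 26% | -0.169 / -0.337 | 0.7% / 0.2% |

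Simulation of the first row gives 4.8% and 8.6%. The 26% in the last row is an assumed value (100 − 74, from the compliance range in the background section), not a forecast. These rates take the ITT difference as the truth.

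**How often the sets could disagree.** At a true ITT difference of -0.5 cm with 10% of laser women only excluded, per protocol alone passes in about 11% (1 cm gap) or 24% (2 cm gap) of trials. With 10% laser and 26% estrogen excluded, ITT alone passes in about 20% or 24%. At the design value of no difference, with 10% excluded per arm, per protocol alone passes in 86.1 − 84.8 = 1.3% (no gap) or 86.0 − 84.0 = 2.0% (2 cm gap).

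**Power at no true difference, per protocol alone and with both sets required:**

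| Scenario | Per protocol | Both |
|---|---|---|
| 83 per arm, 10% excluded per arm, no gap | 86.1% | 84.8% |
| Same, 2 cm gap | 86.0% | 84.0% |
| 98 ITT and 83 per protocol per arm, no gap | 89.4% | 88.5% |
| Same, 2 cm gap | 89.4% | 87.8% |
| 83 per arm, 10% of laser only, 1 cm gap | 92.8% | 88.8% |
| Same, 2 cm gap | 96.1% | 88.3% |

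The two 98/83 rows apply if the plan's 15% already covers treatment drop-outs. In every row ITT is represented by women with a 6-month score. A mixed model on all randomised women was not simulated.

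**The case against.** The plan names one primary set in advance, gives a reason, and commits to an ITT analysis of the same outcome, so a reader of the results would see any conflict. Per-protocol primary with ITT in support is an accepted convention. All of that stands: the test is not invalid. What is missing is any effect of ITT on the conclusion.

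A reader might infer that the per-protocol set is biased towards non-inferiority. The documents do not support that. They state the same condition for both arms, and nothing plans one-sided exclusions. Error above 2.5% appears only in the assumed laser-only scenario; in the other rows of the table per protocol is neutral or stricter.

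A reader might also take the background statement that "compliance rates for estrogen are variable, ranging between 52-74"% to mean that 26 to 48% of estrogen women would be excluded. It does not show this. The rate is undefined, comes from cited literature rather than this trial, and is not the share of participants failing a cut-off that the plan never sets. It can serve only as an assumed value.

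Disagreement at -0.5 cm is likewise not evidence of bias: each analysis alone is far from certain to pass there, so overlapping samples often fall on either side of the limit. At no true difference, with equal exclusions, per protocol alone passes in only 1 to 2% of trials.

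Finally, where a strict adherence cut-off removes many estrogen women, per protocol is the harder hurdle and adding ITT changes almost nothing (66.6% to 66.4% power with 10% laser and 26% estrogen excluded and a 1 cm gap). That is a fair reason to settle the membership rule as well.

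**Conclusion.** The point holds as a gap in the decision rule. Non-inferiority is decided by a post-randomisation subset alone, and ITT could fail -1.0 cm without affecting the claim. That follows from the text and needs no assumption.

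The size of any resulting error does rest on assumptions. In the one unfavourable scenario examined, false non-inferiority rises from 2.5% to about 4.8% or 8.7%. This requires 10% laser-only exclusions, a 1 or 2 cm gap, SD 2.0, 83 per arm, and the ITT difference taken as the truth. The documents give no figure for laser non-completion or for the gap, so neither the direction nor the size can be predicted.

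The missing exposure threshold adds to the uncertainty but would, alone, be a matter of missing detail. This is a worthwhile, inexpensive improvement and not a defect that undermines the trial.

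**What to change.** Keep the per-protocol analysis. State in the Analysis Plan that non-inferiority is concluded only if the lower limit of the two-sided 95% confidence interval for Estrogen minus Laser exceeds -1.0 cm in both the per-protocol set and the ITT set. Define ITT as all randomised women as assigned, including those who could not complete laser. The Calendar of Study Procedures already schedules the dryness scale at 6 weeks, 3 months and 6 months, so a mixed model on those visits is one option for incomplete follow-up.

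As a supporting step, fix one comparable membership rule for both arms before outcome data are seen, using the laser sessions delivered and the compliance log. The threshold is for the sponsor to set, with its power cost in view: with 10% laser and 26% estrogen excluded, per-protocol power alone would be 82.0%, 66.6% or 48.0% for a gap of 0, 1 or 2 cm.

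The cost is a change of wording and no new data. Requiring both sets takes power from about 86% to 84–85% with 10% excluded per arm, or from 89.4% to about 88–89% if the 15% allowance already covers the exclusions. If exclusions fall mainly on the laser arm, power drops to about that of ITT, 88–89%; what is given up there is the advantage gained by excluding those women. The power of a mixed-model ITT analysis should be checked before the rule is adopted.
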